10.5.5 Bone Mineral Density Assessed by DXA Scan

In the primary CSR, a subject has only one post-baseline DXA assessment during the 48-week double-blinded treatment period per protocol amendment 1. The only post-baseline assessment is counted as “week 48” visit regardless of the collected nominal visit name. For patients enrolled before protocol amendment 1, there would be maximum 2 DXA assessments during the 48-week double-blinded treatment period. In this case, if a subject has only one assessment, it is counted as “Week 48” visit; if a subject has two assessments, the first one is counted as “Week 24” visit, and the later one as “Week 48” visit regardless of the collected nominal visit name. The analysis has been done on subjects that have at least two measurements (one baseline and one post-baseline measurement).

For the final CSR, post-baseline is defined as the closest visit at Week 48, Week 96, Week 144 or Week 192 if the assessment is on or prior to the efficacy cutoff. If the assessment occurs after the efficacy cutoff, the assessment will not be included in the reported visit.

Descriptive statistics for BMD and T-score baseline, post- baseline, and change from baseline will be summarized for Week 48/96/144/192 visit. Change from baseline at Week 48/96 will be

analyzed using ANCOVA model with the geographical regions defined at randomization and baseline measurement as covariates for the ITT population.

All the DXA data will be presented in a listing.

10.5.6 Mean Change in Myocardial Iron by T2* MRI

In the primary CSR, a subject has one post-baseline myocardial assessment during the 48-week double-blinded treatment period per protocol. The only post-baseline assessment is counted as “week 48” visit regardless of the collected nominal visit name.

For the final CSR, post-baseline is defined as the closest visit at Week 48, Week 96, Week 144 or Week 192 if the assessment is on or prior to the efficacy cutoff. If the assessment occurs after the efficacy cutoff, the assessment will not be included in the reported visit.

Descriptive statistics for myocardial iron measurements and change from baseline will be summarized for Week 48/96/144/192 visits. The 48-week myocardial iron change from baseline will be analyzed only for Weeks 48 and 96 using an ANCOVA model with the geographical regions defined at randomization and baseline myocardial iron as covariates for the ITT population.

A shift table representing the shift from the baseline to the category (≤ 10 and > 10) of Week 48/96/144/192 will be provided for Myocardial Iron T2* value.

A histogram plot of myocardial iron by T2* will be provided for baseline and week 48/96/144/192. All the myocardial iron data will be presented in a listing.

10.5.7 Duration of Transfusion Burden Reduction

The duration of the longest continuous 12-week based erythroid response (based on 33% and 50% criteria) during the entire study period up to the efficacy cutoff will be summarized by the Kaplan–Meier method (LOGLOG transformation will be used). The 33% response is defined as subjects with $\geq 33\%$ reduction from baseline in RBC transfusion burden with a reduction of at least 2 units. The 50% response is defined as subjects with $\geq 50\%$ reduction from baseline in RBC transfusion burden with a reduction of at least 2 units. The median duration of response, 25th and 75th quartiles with the associated 2-sided (at 0.05 alpha level) 95% CIs will be presented for each treatment group. The min and max of duration will be provided for all responders. The Kaplan-Meier plots of the response duration, defined as time from the start of the longest response to end of the response (see below) will also be provided. Only subjects who achieve a response will be included in the analysis.

The duration of the individual continuous response is defined as Last Day of Response – First Day of Response + 1, where

First Day of Response = the first day of the first 12-week interval when the subject meets response,

Last Day of Response = the last day of the last 12-week interval when the subject meets response.

The subject must meet response on all the days within the above duration.

For subjects who have one response and continue to respond at the efficacy cutoff date, the end day of the response will be censored at the date of efficacy cutoff and the duration of response will be calculated as date of efficacy cutoff – first day of response + 1, where date of efficacy cutoff is defined in Section 10.

For subjects who have multiple responses and the last one continues to respond at the efficacy cutoff date, the longest response will be the last one if the duration from response start to censoring is longer than all the previously occurred response durations. If the continuing response duration is not the longest compared with the previously occurred responses, the response with longest duration will be selected. Summary statistics will be provided for total duration of transfusion burden reduction (33% and 50% criteria) within the entire study period and the ratio of total response duration versus entire study duration. The entire study duration is defined as period from day 2 to date of efficacy cutoff.

10.5.8 Time from First Dosing Date to the First Erythroid Response

The descriptive statistics for the time from first dosing date to the first erythroid response (for both 33% and 50% criteria) will be provided by treatment group, where time from first dosing date to the first erythroid response is defined as First Day of Response – Date of First Study Drug +1. The difference in time from first dosing date to the first erythroid response (luspatercept – placebo), corresponding 95% CI and p-value will be calculated by t-test.

Only subjects who have a response will be included.

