## 9.6. Efficacy Analysis

### 9.6.1. Primary Efficacy Analysis

The efficacy analysis will be performed on the ITT population. The primary efficacy analysis will be performed based on 24 weeks of data after all subjects have completed the double-blind 24-week treatment period phase or discontinued before reaching 24 weeks of double-blind treatment (for this study one month equal to 4 weeks is considered). A higher response rate in the luspatercept over placebo and a p-value < 0.05 will confirm the superiority of luspatercept in the efficacy.

The primary efficacy endpoint of this study is defined as subjects with  $\geq 33\%$  reduction from baseline in RBC transfusion burden with a reduction of at least 2 units from Week 13 to Week 24 compared to the 12-week interval prior to randomization for luspatercept plus BSC versus placebo plus BSC.

For the early discontinued subjects, ie, who did not complete 24 weeks of double-blinded treatment period, the transfusion records will still be collected up to 48 weeks. All the transfusion records will be used to evaluate primary and secondary endpoints.

The first day to be used for statistical analysis will be defined as the date of the first dose. A transfusion received on Dose 1 Day 1 will be counted in the baseline transfusion burden.

The primary endpoint response rate is calculated using the number of responders divided by all subjects in the ITT population. The response rates of the subjects who randomized to luspatercept and the placebo will be calculated. Let  $P_1$  denote the true response rate in the luspatercept group, and  $P_2$  denote the true response rate in the placebo group. In the primary efficacy analysis, the statistical hypothesis is

$$H_0 : P_1 = P_2$$

$$H_a : P_1 \neq P_2$$

The number and percentage of subjects in the ITT population who achieve the response will be calculated for luspatercept and placebo. The difference in proportions between luspatercept and placebo will be calculated and the Cochran Mantel-Haenszel (CMH) chi-square test would be performed using randomization factors as strata, corresponding 95% confidence interval (CI)

associated with the test will be provided. A higher response rate in the luspatercept arm over placebo arm with a p-value < 0.05 will infer that luspatercept is significantly superior to placebo.

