4.2.2.3 Extended Secondary Efficacy Endpoints

Extended secondary efficacy endpoints will include:

- Mean change from baseline in liver iron concentration (LIC, mg/g dw) by MRI up to final database lock
- Mean change from baseline in mean daily dose of ICT up to final database lock
- Mean change from baseline in serum ferritin up to final database lock
- Mean change from baseline in total hip and lumbar spine BMD by DXA up to final database lock
- Mean change from baseline in myocardial iron by MRI up to final database lock

- Healthcare resource utilization up to final database lock
- Proportion of subjects who are transfusion independent for ≥ 8 weeks during treatment up to final database lock
- Duration of reduction in transfusion burden up to final database lock
- Duration of transfusion independence up to final database lock
- Time to erythroid response up to final database lock
- Post-baseline transfusion event frequency versus placebo up to final database lock

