10. EFFICACY ANALYSIS

All efficacy evaluations are conducted using the ITT population, with the exception of Quality of Life analyses that are conducted on the HRQoL evaluable population. Statistical comparisons are made between luspatercept plus BSC vs. placebo plus BSC. Key secondary efficacy results are considered statistically significant after consideration of the strategy for controlling the family-wise Type 1 error rate, as described in Section 10.1, Multiplicity. All statistical tests are 2-sided at the significance level of $\alpha = 0.05$, and the corresponding p-values and 2-sided CIs for point estimates are reported, unless specified otherwise.

For the early treatment discontinued subjects, i.e., patients who did not complete 24 weeks or 48 weeks of double-blinded treatment period, the transfusion records were collected up to 48 weeks or 9 weeks post last dose, whichever was the later date. All the transfusion records collected throughout the entire study period up to the efficacy cutoff date were used in the RBC related efficacy analyses. The efficacy cutoff date for the primary CSR was defined as the minimum date among death date, study discontinuation date, last dose date + 20, and 11MAY2018. For the primary and key secondary endpoints, if at the time of data summary, a subject's efficacy cutoff date was before the end of the 12-week interval or a subject had any invalid transfusion records (i.e., transfusion unit not available) during the specified 12-week interval, this subject was included in the analysis as a non-responder.

All the efficacy analysis for the final CSR will not include the assessments for the placebo patients who crossed over to luspatercept. In other words, the assessments for the placebo patients will be analyzed up to the cross-over timepoint. For those subjects in the original luspatercept treatment, their assessments will be analyzed until the new efficacy cutoff date which is defined as the minimum date among death date, study discontinuation date, last dose date + 20.

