10.5 Other Extended Efficacy Analyses

In general, descriptive statistics will be provided and statistical tests will be applied if appropriate. For continuous variables, LS means with corresponding SEs for each treatment group, along with LS mean of treatment difference (luspatercept versus placebo) with corresponding 95% CI and p-value will be presented for ANCOVA method. Kaplan-Meier methods will be used to analyze time to event variables. Counts and percentages will be used to describe categorical variables. If an ANCOVA method is used, the statistical assumption will be validated first, log transformation will be applied as needed.

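### The t-test on time to first response in SAP 10.5.8 (responders only, follow-up that differs by arm) is not a valid treatment comparison and should be deleted

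*SAP*

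**What the plan says.** - **The test.** SAP 10.5.8 describes time from first dose to first response (33% and 50% criteria) by arm. It then adds a luspatercept-minus-placebo difference, with "corresponding 95% CI and p-value will be calculated by t-test". It continues: "Only subjects who have a response will be included". It does not say whether the t-test is pooled or Welch, and it gives no common window and no handling of non-responders.
- **The reporting period.** SAP 4.2.2.3 lists "Time to erythroid response up to final database lock" for the final CSR. SAP 10.5.1 searches every rolling 12-week window up to the efficacy cutoff.
- **The cutoffs.** Under SAP section 10, "the assessments for the placebo patients will be analyzed up to the cross-over timepoint". Subjects originally on luspatercept count until the "new efficacy cutoff date which is defined as the minimum date among death date, study discontinuation date, last dose date + 20".
- **The general rule.** SAP 10.5 states that "Kaplan-Meier methods will be used to analyze time to event variables". Section 10.5.8 is a specific exception, and no reason is given for it.
- **The protocol.** Section 9.6.3.9 also restricts the endpoint to responders, but plans only descriptive summaries by arm, from the double-blind phase.

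**The concern.** There are two separate faults.

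1. **Selection.** Whether a subject responds is known only after randomisation and may depend on treatment. The responders in the two arms are therefore not randomised groups, even with equal follow-up. A p-value attached to their difference does not say whether luspatercept brings response sooner.
2. **Unequal follow-up.** The luspatercept arm can collect first responses long after the placebo arm has stopped contributing. Each one lengthens the luspatercept mean and has no placebo counterpart. If first responses are all early, this second fault disappears; if some are late, the difference is pushed against luspatercept.

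At stake is one nominal p-value and interval in the final CSR that a reader could take as evidence on speed of response.

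**Working it through.** **1. The plan's own figures.** SAP 10.5.8 states no number. The only related design figure is the sample size in SAP 4.4. With 40% vs 20%, 2:1 allocation, two-sided 0.05, 90% power and a continuity correction, the two-proportion formula gives 90 placebo and 270 in total; 270 / 0.90 = 300. It reproduces and is not at issue. At those rates the t-test would compare 200 × 0.40 = 80 selected luspatercept subjects with 100 × 0.20 = 20 selected placebo subjects.

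**2. The follow-up gap.** SAP 10.5.7 dates a response to the first day of its 12-week window, so follow-up of F weeks can show first responses only up to week F − 12. SAP 5.1 defines windows to Week 228, which gives 216 weeks. The documents give no cross-over times. The latest placebo LIC visit analysed is Week 96 (SAP 10.5.2), which gives 84 weeks. On those two limits, 216 − 84 = 132 weeks are open to luspatercept only.

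**3. Hand calculation of the bias, no treatment effect.** Assumed for both arms: 60% respond early with mean 6 weeks, and the rest have a late-response hazard of 0.02 per 12 weeks (1/600 per week). Assumed follow-up: placebo 96 weeks, luspatercept uniform 48–228 weeks.
- Placebo: late share among the other 40 subjects = 1 − e^(−84/600) = 0.131, or 5.2 subjects. Their mean time = 600 − 84e^(−0.14)/(1 − e^(−0.14)) = 41.0 weeks. Responder mean = (60 × 6 + 5.2 × 41.0) / 65.2 = 8.8 weeks.
- Luspatercept: late share among the other 80 = 1 − (e^(−0.06) − e^(−0.36))/0.30 = 0.1864, or 14.9 subjects. Their mean time = [600 − (600/180)(1236e^(−0.06) − 1416e^(−0.36))] / 0.1864 = 12.96 / 0.1864 = 69.5 weeks. Responder mean = (120 × 6 + 14.9 × 69.5) / 134.9 = 13.0 weeks.
- False difference: 13.0 − 8.8 = 4.2 weeks against luspatercept.

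**4. False significantly slower results, no treatment effect.** Simulated trials of 200 vs 100 with the same early-responder model; pooled / Welch. An unbiased test gives about 2.5% in this direction.

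| Late hazard per 12 weeks | Placebo to 96 weeks | Placebo uniform 48–96 weeks |
|---|---|---|
| 0 | 2% / 3% | 2% / 3% |
| 0.01 | 4% / 19% | 7% / 31% |
| 0.02 | 12% / 33% | 28% / 59% |
| 0.05 | 30% / 50% | 67% / 87% |

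These runs let non-responders stay on treatment. If subjects without a response by Week 36 stop treatment instead, the 48–96 week column falls to about 2–4% / 5–8% when they stop by about Week 96. It falls to 2% / 7%, 4% / 9% and 7% / 14% when they stop between Weeks 48 and 120. A log-rank test in all subjects rejects in 4.4–5.4% of null trials.

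**5. True benefit.** Assumed: 40% vs 20% early responders (the SAP 4.4 rates, which are Week 13–24 rates, borrowed here).
- No late responses: responder means are 6.0 vs 6.0 weeks.
- Placebo to 96 weeks: means are 19.9 vs 18.2 weeks at late hazard 0.02 and 27.4 vs 24.1 at 0.05. A significant reversal occurs in at most about 2% / 10%.
- Placebo 48–96 weeks: means are 19.9 vs 12.9 and 27.4 vs 17.1 weeks. Reversal occurs in 4% / 32% and 22% / 59%.

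**The case against.** The case for leaving the section alone has real substance.

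- **Low stakes.** The endpoint is outside the gatekeeping sequence (SAP 10.1, 10.3), and the primary and key secondary analyses are closed. The follow-up bias runs against luspatercept, so it cannot create a false efficacy claim. This stands and limits the importance of the point.
- **Tests are allowed.** Protocol 9.6.3 and SAP 10.5 permit tests where appropriate, the protocol too uses responders only, and the SAP extends the endpoint openly. A reader might infer a breach of the protocol. The documents do not support that. Protocol Table 2 names the double-blind Treatment Period but also marks Long-Term, and the double-blind phase in 9.6.3.9 can include the double-blind Long-term Treatment Period. Even so, permission for appropriate tests does not cover this one.
- **Reversal.** A reader might infer that the test will show luspatercept as slower despite a benefit. That rests mainly on the 48–96 week pattern, which leaves no placebo subject followed beyond Week 96. Yet the SAP plans Week 96 between-arm models for LIC, chelation dose, ferritin, bone density and myocardial iron. It also ignores that luspatercept non-responders who stop treatment leave the data.
- **Missed benefit.** A reader might infer that the t-test lacks power, since a log-rank test finds the 40% vs 20% benefit far more often. But with no late responses, responders in the two arms are equally fast and the t-test is right to find nothing. The benefit lies in the share responding, which the CMH analyses already test.

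**Conclusion.** The point holds. The planned difference, interval and p-value compare subsets selected after randomisation over arm-specific follow-up, so they are not a valid treatment comparison. The selection fault needs no assumption about timing. The follow-up bias is toward luspatercept looking slower, and its size cannot be fixed from the documents: actual cross-over times, luspatercept follow-up and late-response rates are not given. Under no effect, false slower results range from about the nominal level (no late responses, or non-responders stopping early) to about 30% / 50% with placebo at 96 weeks, and 67% / 87% with placebo at 48–96 weeks. With a true benefit and placebo at 96 weeks, a significant reversal is uncommon.

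It should be corrected because the misleading output is avoidable, not because any main conclusion is at risk. The SAP of 19 June 2018 is not among the documents, so nothing can be said about whether the primary CSR used the same test.

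**What to change.** **Needed.** Delete the t-test difference, confidence interval and p-value from SAP 10.5.8. Keep responder times as descriptive statistics by arm, labelled as not a between-arm comparison. This is enough on its own, returns to the descriptive approach of Protocol 9.6.3.9, and needs no new data or programming.

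**Optional, only if a comparison is wanted.**
- Use all ITT subjects over a window common to both arms, for example 12-week windows ending by Day 337.
- Show Kaplan-Meier curves with a log-rank test stratified by region, and label the p-value as nominal.
- Censor non-responders at the start of their last evaluable window (cutoff − 83 days; Day 1 if there is none). For Day 337 this is 337 − 83 = Day 254, the first day of the Week 37–48 interval in SAP 5.1.
- State that this tests response share and speed together, and that censoring at last dose + 20 days may be informative.
- As a sensitivity analysis, drop the last-dose cutoff within 48 weeks. The data exist: for early discontinuations, Protocol 9.6.1 says "the transfusion records will still be collected up to 48 weeks", and SAP section 10 says "the transfusion records were collected up to 48 weeks or 9 weeks post last dose, whichever was the later date".

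**Cost of the option.** It needs SAP wording and one standard time-to-event program. Extended-period data become supportive for the comparison. At the planned 10% drop-out, if every drop-out is a never-responder censored at Day 1, the Kaplan-Meier response rises from 40% to 0.40 / 0.90 = 44.4% and from 20% to 0.20 / 0.90 = 22.2%.

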10.5.9 Transfusion Independence

The number and percent of subjects who achieve transfusion independence will be summarized by treatment group and the treatment comparison will be analyzed using the CMH model stratified by the geographical regions defined at randomization. Transfusion independence is defined as the absence of any transfusion during any consecutive “rolling” 6-week, or 8-week or 12-week time interval within the entire study period up to the efficacy cutoff date, i.e., Day 2 to 43, Day 3 to 44, ..., Day x to efficacy cutoff date for 6-week interval (or Day 2 to 57, Day 3 to 58, ..., Day x to efficacy cutoff date for 8-week interval, or Day 2 to 85, Day 3 to 86, ..., Day x to efficacy cutoff date for 12-week interval). Subjects whose efficacy cutoff date that is before day 43 (for 6-week based), or day 57 (for 8-week based) or day 85 (for 12-week based) will be counted as non-responders.

The duration of transfusion independence will be summarized by the Kaplan–Meier method. The median duration of response, 25th and 75th quartiles with the associated 2-sided (at 0.05 alpha level) 95% CIs will be presented for each treatment group. The min and max of duration will be provided

for all responders. The Kaplan-Meier plots of the transfusion independence duration, defined as time from first response to end of response (see below) will also be provided. Only subjects who achieve a response will be included in the analysis.

The duration of transfusion independence will be calculated similar to the duration of erythroid response, which is defined as Last Day of Response – First Day of Response +1,

where

First Day of Response = the first day of the first 6-week (or 8-week or 12-week) interval when the subject meets response,

Last Day of Response = the last day of the last 6-week (or 8-week or 12-week) interval when the subject meets response.

For subjects who continue to respond at the efficacy cutoff date, the end day of the response will be censored at the date of efficacy cutoff and the duration of response will be calculated as date of efficacy cutoff – first day of response +1, where date of efficacy cutoff is defined in Section 10.

